### **3.1.5 Independent Review Committee**

An IRC will assess all patients for response on the basis of imaging results and bone marrow biopsy results. The review will consist of two parts: a radiology review and an oncology review. The IRC will consist of radiologists, nuclear medicine experts, and a board certified oncologist with experience in malignant lymphoma. Specific methodological and operational details will be specified in the IRC charter.

### **3.1.6 Post-Treatment and Survival Follow-Up**

Patients who complete treatment or discontinue treatment for reasons other than disease progression will undergo assessments every 3 months during the post-treatment follow-up period, which will continue until disease progression, the start of new anti-lymphoma treatment, or the end of the study (as defined below), whichever occurs first. Patients who experience disease progression will be evaluated for survival status and new anti-lymphoma treatment every 3 months until the end of the study. Details are provided in the schedules of assessments (see [Appendix 1](#) and [Appendix 2](#)).

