### **3.1.3 Expansion Phase (Part 2)**

The expansion phase is designed to further assess the safety and efficacy of obinutuzumab in combination with idasanutlin at the RP2D *with the selected regimen in patients with R/R FL and of rituximab in combination with idasanutlin at the RP2D in patients with R/R DLBCL*. Approximately 80 patients (40 patients with R/R FL and 40 patients with R/R DLBCL) will be enrolled during the expansion phase and treated as described below. *The start of the expansion phase may not happen simultaneously for the two indications.*

All patients will receive 6 cycles of induction treatment, administered in 28-day cycles, as outlined in [Table 6](#). Patients with FL who achieve a CR or PR at the EOI will receive maintenance treatment with obinutuzumab and idasanutlin. *Patients with DLBCL who achieve a CR or PR at the EOI will receive consolidation treatment with rituximab and idasanutlin. Post-induction treatment should start 8 weeks ( $\pm 1$  week) after Day 1 of the final cycle of induction and will continue until disease progression or unacceptable toxicity for up to 2 years for maintenance treatment and 6 months for consolidation treatment (see [Table 7](#)).*

*Patients with DLBCL who achieve a CR based on modified Lugano 2014 criteria at the end of induction (defined as within 6-8 weeks after the start of the last cycle of study treatment) are allowed to proceed to hematopoietic stem cell transplantation if deemed appropriate by the investigator. Such patients will be followed for disease progression and survival.*

The schedules of assessments are provided in [Appendix 1](#) and [Appendix 2](#), and a study schema is provided in [Figure 6](#).

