## **3.2 END OF STUDY AND LENGTH OF STUDY**

The end of this study is defined as the time when both of the following conditions are met:

- All enrolled patients with FL have completed or discontinued maintenance treatment, and
- All enrolled patients with DLBCL have been followed for at least 1 year after they have completed or discontinued *study treatment (including induction treatment and consolidation treatment, as applicable)*.

The total length of the study, from screening of the first patient to the end of the study, is expected to be approximately 48 months.

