#### **5.3.1 Adverse Event Reporting Period**

Investigators will seek information on adverse events at each patient contact. All adverse events, whether reported by the patient or noted by study personnel, will be recorded in the patient's medical record and on the Adverse Event eCRF.

**After informed consent** has been obtained **but prior to initiation of study treatment**, only serious adverse events caused by a protocol-mandated intervention (e.g., invasive procedures such as biopsies, discontinuation of medications) should be reported (see Section 5.4.2 for instructions for reporting serious adverse events).

**After initiation of study treatment**, all adverse events will be reported until 90 days after the last study treatment. After this period, the investigator should report any serious adverse events that are believed to be related to prior study drug treatment.

An exception is made for Grade 3 or 4 infections (related and unrelated) *in patients who received obinutuzumab*, which should be reported up to 2 years after the last dose of *obinutuzumab*.

*Second malignancies will be recorded indefinitely for patients who received obinutuzumab (even if the study has been closed) (see Section 5.6).*

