#### **5.3.5.8 Deaths**

For this protocol, mortality is an efficacy endpoint. Deaths that occur during the protocol-specified adverse event reporting period (see Section 5.3.1) that are attributed by the investigator solely to progression of lymphoma should be recorded only on the Study Completion/Early Discontinuation eCRF. All other on-study deaths, regardless of relationship to study treatment, must be recorded on the Adverse Event eCRF and immediately reported to the Sponsor (see Section 5.4.2). An IMC will monitor the frequency of deaths from all causes.

Death should be considered an outcome and not a distinct event. The event or condition that caused or contributed to the fatal outcome should be recorded as the single medical concept on the Adverse Event eCRF. Generally, only one such event should be reported. If the cause of death is unknown and cannot be ascertained at the time of reporting, "**unexplained death**" should be recorded on the Adverse Event eCRF. If the cause of death later becomes available (e.g., after autopsy), "unexplained death" should

be replaced by the established cause of death. *The term "sudden death" should not be used unless combined with the presumed cause of death (e.g., "sudden cardiac death").*

During survival follow-up, deaths attributed to progression of lymphoma should be recorded only on the Study Completion/Early Discontinuation eCRF.

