## Appendix 1 Schedule of Activities for Patients with Follicular Lymphoma (Dose-Escalation and Expansion) (cont.)

- 
- a The screening period starts with the signing of the Informed Consent Form. Results of standard-of-care tests or examinations performed prior to obtaining informed consent and within the defined window may be used as screening and baseline assessments; such tests do not need to be repeated for screening purposes.
- b Patients who complete maintenance treatment or discontinue maintenance treatment prematurely will undergo assessments at EOM.
- c EOI assessments should be performed 6•8 weeks after Day 1 of the last induction cycle. As an exception, patients who discontinue induction treatment prematurely because of an adverse event may undergo EOI assessments 4•8 weeks after their last dose of study treatment.
- d Patients who complete treatment or discontinue treatment for reasons other than disease progression will undergo assessments every 3 months during the post-treatment FU period, which will continue until disease progression, the start of new anti-lymphoma treatment, or the end of the study, whichever occurs first. The first post-treatment FU visit is 3 months after the EOI visit for patients who do not receive maintenance treatment and 3 months after the last dose for patients who receive maintenance treatment. Patients who experience disease progression will undergo limited assessments every 3 months during the survival FU period, which will continue until the end of the study. The end of the study is defined as the time when all enrolled FL patients have completed or discontinued study treatment and all enrolled DLBCL patients have been followed for at least 1 year after they have completed or discontinued study treatment.
- e Informed consent must be documented before any study-specific screening procedure is performed.

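### Patients who start new anti-lymphoma treatment without progression have no scheduled survival contact: a minor gap that one clause in three places would close

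*Combined protocol and SAP*

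**What the plan says.** Section 3.1.6 sets up two periods after treatment. The first is a 3-monthly post-treatment period for patients who finish or stop treatment without progression, "which will continue until disease progression, the start of new anti-lymphoma treatment, or the end of the study", whichever comes first. The second is survival follow-up, and its entry rule names one group: "Patients who experience disease progression will be evaluated for survival status and new anti-lymphoma treatment every 3 months until the end of the study".

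Appendix 1 footnote d (FL) has the same structure: "Patients who experience disease progression will undergo limited assessments every 3 months during the survival FU period". Appendix 2 footnote e (DLBCL) repeats it. In both schedules the survival row is marked only under the survival follow-up column.

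Other sections bear on the gap:

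- Sections 3.1.2.2 and 3.1.3, for DLBCL patients in CR who go to transplantation: "Such patients will be followed for disease progression and survival". No interval is given.
- Section 3.2 ends the study only once all DLBCL patients "have been followed for at least 1 year after they have completed or discontinued" study treatment. The FL condition is "All enrolled patients with FL have completed or discontinued maintenance treatment", with no follow-up required afterwards.
- Section 5.3.1: "all adverse events will be reported until 90 days after the last study treatment". Section 5.3.5.8 has deaths due solely to lymphoma entered on the study completion form, and then: "All other on-study deaths, regardless of relationship to study treatment, must be recorded on the Adverse Event eCRF".
- Section 6.4.3 censors OS at the date last known alive. It lists new therapy as an EFS event in its own right.

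**The concern.** A patient who starts new therapy without progression leaves the first period and is not assigned to the second. The plan makes such patients foreseeable. Its EFS definition separates new therapy from progression. Only CR or PR at the end of induction leads to post-induction treatment, so a patient with stable disease comes off study treatment without having progressed. Sections 3.1.2, 4.6.2 and 5.1.5 also require permanent discontinuation for several toxicities and for long delays.

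OS for these patients would be censored around the switch of therapy. The reason for switching may be related to prognosis, so the censoring may be informative. The direction cannot be told in advance: patients switched for an inadequate response may do worse than the rest, and those given effective next-line therapy may do better.

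**Working it through.** **1. The rules side by side**

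| Why post-treatment follow-up ends | Assigned to 3-monthly survival follow-up? |
|---|---|
| Progression | Yes (3.1.6; Appendix 1 note d; Appendix 2 note e) |
| New therapy, no progression, FL | No |
| New therapy, no progression, DLBCL | No visit schedule. Follow-up is promised after transplantation in CR (3.1.2.2, 3.1.3), and at least 1 year is implied by 3.2 |
| End of study | Not applicable |

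**2. How long deaths are captured anyway**

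Day 0 is Cycle 1 Day 1 and a month is 30.44 days. Deaths are recorded to 90 days after the last dose.

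- Last dose in Cycle 6 (Day 5, day 144): 144 + 90 = day 234, month 7.7.
- Last dose in Cycle 2 (Day 5, day 32): 32 + 90 = day 122, month 4.0.
- DLBCL consolidation completed, 6 months from about day 196: 196 + 182.6 + 90 = about day 469, month 15.4.
- FL maintenance completed, up to 24 months from about day 196: past month 24.

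**3. Size of the OS error at 24 months**

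The documents give neither the affected share nor the later hazard. Assumed: exponential OS with median 24 months, so h = ln 2 / 24 = 0.0289 per month; a share p affected; capture of deaths ending at month d; and a hazard for affected patients after d that is HR times that of the others. The reported curve follows the patients still observed, so

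error = S(d) × p × [exp(-(24-d)h) - exp(-(24-d)h × HR)],

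where a positive value means reported OS is too high.

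- d = 7.7: S(d) = 0.801. The exponentials are 0.625 (others), 0.390 (HR 2) and 0.790 (HR 0.5).
- d = 4.0: S(d) = 0.891. The exponentials are 0.561, 0.315 and 0.749.

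| Capture ends | p | HR 0.5 | HR 2 |
|---|---|---|---|
| Month 7.7 | 10% | -1.3 | +1.9 |
| Month 7.7 | 20% | -2.7 | +3.8 |
| Month 4.0 | 10% | -1.7 | +2.2 |
| Month 4.0 | 20% | -3.3 | +4.4 |

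For example, at d = 4.0, p = 20% and HR 2: 0.891 × 0.20 × (0.561 - 0.315) = 0.044.

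For completed consolidation (d = 15.4, p = 20%), S(d) = 0.641 and the exponentials are 0.780, 0.609 and 0.883, which gives -1.3 to +2.2 points. For completed FL maintenance the 24-month error is nil.

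**4. Cross-check by simulation**

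With n=40, median OS of 24 months, censoring at months 6 to 12 and a doubled later hazard, 24-month OS was overstated by 1.7 points with 4 patients affected and 3.5 points with 8. With an unchanged hazard there was no bias beyond simulation noise.

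**5. Yardstick**

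The 95% half-width at 50% survival with n=40 is 1.96 × √(0.5 × 0.5 / 40) = 15.5 points.

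**The case against.** The strongest reply is that this hardly matters. PFS, EFS and OS are exploratory and summarized descriptively, no decision depends on them, and the worst error above is under a third of the sampling half-width. That stands, and it is why the point is minor.

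The protocol also has partial safeguards. The 90-day window moves later with maintenance or consolidation. After obinutuzumab, Grade 3 or 4 infections are reported for 2 years and second malignancies indefinitely (5.3.1, 5.6). Section 4.6.1 mentions public records as a source of survival status. These limit the loss but do not replace scheduled contact: the infection and malignancy rules catch only some causes of death, and the public-records sentence sits in the paragraph on withdrawal of consent.

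One could also argue that a patient who switches therapy and later progresses qualifies for survival follow-up at that point. But once post-treatment follow-up has stopped, no scheduled assessment would reveal the progression.

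Three stronger readings are tempting and are not supported:

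- **That these patients have no survival follow-up at all.** Sections 3.1.2.2, 3.1.3 and 3.2 state commitments for DLBCL, and early deaths are captured in both diseases. What is missing is a schedule.
- **That PFS handling of deaths after new therapy is undefined.** Section 6.4.3 counts death from any cause and does not censor at new therapy, so such deaths already count.
- **That the 6-month PFS/EFS landmark must be moved.** It does coincide with the opening of the end-of-induction scan window: Cycle 6 Day 1 is day 140, so the window is days 182 to 196, and 6 months is day 182.6. But dating progression at detection is conventional, and Section 4.5.5.1 requires a scan whenever progression is suspected, so the size of any excess cannot be established and may be nil. A 7-month landmark (day 213) is not safe either, because one 21-day delay moves the window to days 203 to 217.

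**Conclusion.** The gap is real and appears consistently in three places of the current text. Followed as written, the plan stops scheduled survival contact for patients who start new therapy without progression. FL is the main group affected; for DLBCL the difficulty is a follow-up commitment with no visits behind it.

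The consequence is small. For patients whose last dose was in induction, the 24-month OS error is about -3.3 to +4.4 points across the assumed range, and it is smaller or nil after maintenance or consolidation. The affected share, median OS and hazard ratio are all assumptions. The primary endpoint, CR at the end of induction by independent review, is untouched, as is the sample size. This is a minor improvement, worth making because the remedy is cheap and survival status is easier to collect prospectively than to reconstruct.

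**What to change.** In Section 3.1.6, Appendix 1 footnote d and Appendix 2 footnote e, state that patients who experience disease progression or start new anti-lymphoma treatment enter the existing 3-monthly survival follow-up. This also gives the DLBCL commitments in Sections 3.1.2.2, 3.1.3 and 3.2 a visit schedule.

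The cost is one clause in three places and a few more survival contacts, with no added scans. Section 6.4.3 needs no change. When the 6-month PFS and EFS figures are reported, a note that the landmark falls as the end-of-induction scan window opens would be enough.

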## **3.2 END OF STUDY AND LENGTH OF STUDY**

The end of this study is defined as the time when both of the following conditions are met:

- All enrolled patients with FL have completed or discontinued maintenance treatment, and
- All enrolled patients with DLBCL have been followed for at least 1 year after they have completed or discontinued *study treatment (including induction treatment and consolidation treatment, as applicable)*.

The total length of the study, from screening of the first patient to the end of the study, is expected to be approximately 48 months.

## **3.3 RATIONALE FOR STUDY DESIGN**

### **3.3.1 Rationale for Treatment Combination**

MDM2 regulates p53 through a negative feedback loop. However, in cancer cells overexpressing MDM2, this feedback loop is dysregulated. Therefore, blocking the

p53-MDM2 interaction is expected to overcome the oncogenic consequences of MDM2 overproduction and to restore p53 function (Ray-Coquard et al. 2012).

A class of imidazoline compounds was identified as potent and selective inhibitors of the p53-MDM2 interaction (Vassilev et al. 2004). These molecules, termed nutlins, interact specifically with the p53-binding pocket of MDM2, and, thus, free p53 from negative feedback mechanisms. Idasanutlin binds selectively to the p53 site on the surface of the MDM2 molecule in vitro with high affinity and can effectively displace p53 from MDM2, leading to stabilization and accumulation of p53 protein and activation of the p53 pathway. The compound has good oral bioavailability and has shown TGI in two different NHL mouse xenograft models tested at doses that did not cause noteworthy toxicity. However, its efficacy as a monotherapy in these mouse models is very inferior to combination with other drugs, especially obinutuzumab.

Obinutuzumab and rituximab have been shown to be safe and active as monotherapy in patients with R/R NHL (Section 1.2.2).

Based on the fact that the majority of B-lymphoid malignancies, including NHL and CLL, bear wild-type p53, and the complementary mechanisms of action involving increased apoptosis (MDM2 antagonists) or direct cell death (obinutuzumab and rituximab), the combination of an anti-CD20 antibody (obinutuzumab or rituximab) and a MDM2 antagonist has the potential for superior efficacy compared to single-agent treatment in treating B-lymphoid malignancies. The combination of obinutuzumab or rituximab with the MDM2-antagonist idasanutlin resulted in enhanced cell death of p53 wild-type NHL tumor cells. Therefore, the complementary mechanism of actions of these drugs promises additive effect and, there are first attempts to quantify cooperative effects in system biology based PD model. In fact, combinatorial efficacy of different pro-apoptotic drugs in NHL can be described in a quantitative way by a signaling model of CD20 pharmacodynamics (Harrold et al. 2012).

[figure not shown]
A xenograft model of MCL shows more durable response only in idasanutlin in combination with the anti-CD20 drug obinutuzumab (see Section 1.3.1, Figure 2). The addition of obinutuzumab or rituximab to idasanutlin may primarily prevent relapse. Enhanced tumor control in the Z-138 MCL and a high bar DLBCL xenograft model was observed with an obinutuzumab or rituximab plus idasanutlin combination over idasanutlin monotherapy or an anti-CD20 antibody alone (see Section 1.3.1). These data support further evaluation of the combination of idasanutlin and obinutuzumab or rituximab in clinical studies in lymphoma.

### **3.3.2 Rationale for Idasanutlin Starting Dose**

Based on data from Studies NP27872 and NP28679 in solid tumors and AML, the first PD signal was detected at an AUC24 between 50 and 60 • g • hr/mL. For the QD • 5 days regimen (see Figure 8), 55 • g•hr/mL (55,000 ng • hr/mL) corresponds to a daily dose of

approximately 100 mg of the idasanutlin SDP formulation, which is equivalent to 200 mg of the MBP formulation (see Figure 5 for conversion).

**Figure 8 PD Biomarker Defines Doublet Starting Dose of Idasanutlin (MBP)**

AUC=area under the concentration time•curve; d=day; MIC-1=macrophage inhibitory cytokine 1; MBP= microprecipitated bulk powder; PD=pharmacodynamic.

In addition, safety data are available for patients with solid tumors and NHL who received the idasanutlin MBP formulation. For the 200-mg MBP QD•5 schedule, no Grade 3 or 4 hematologic or related gastrointestinal toxicities were observed.

Therefore, a daily dose of 100 mg of the idasanutlin SDP formulation, which is roughly the equivalent of 200 mg idasanutlin MBP formulation, seems to be a safe starting dose with potential to activate p53 as determined by the MIC-1 PD Marker in combination with obinutuzumab *or rituximab*.

### 3.3.3 Rationale for Dosing Regimen

There is a standard regimen for obinutuzumab used in all pivotal NHL studies of a fixed dose of 1,000 mg (see the Obinutuzumab Investigator’s Brochure) in combination with several cytotoxic drugs. These data support this efficacious fixed dose as the basis for combinations of obinutuzumab with targeted drugs. Obinutuzumab at a fixed dose of 1,000 mg is also being studied in combination with other targeted agents in a number of ongoing clinical studies, including MPDL3280A (GO29383), polatuzumab vedotin (GO27834), and venetoclax (GP28331, GO27878).

*The study will start with obinutuzumab standard dosing in combination with idasanutlin from Cycles 1 to 6 (Regimen A). For patients with FL, an alternative dosing regimen (Regimen B) with obinutuzumab given at Cycle 1 followed by obinutuzumab in combination with idasanutlin from Cycles 2 to 6 will be explored (bridging cohorts) to investigate the possibility of alleviating hematological toxicities at Cycle 1. The rationale for exploring Regimen B in patients with FL is that obinutuzumab is given 3 times during Cycle 1 (Days 1, 8, and 15) compared to only on Day 1 in subsequent cycles. Those 3 doses of obinutuzumab, when combined with idasanutlin at higher doses in the same treatment cycle, may induce more profound hematologic toxicities. Staggered idasanutlin dosing to start at Cycle 2 may mitigate toxicities and allow recovery before dosing with the combination. Only one regimen will be chosen for the expansion phase.*

*The dose of rituximab of 375mg/m^2 is the recommended dose in the NHL population and is the standard of care. For DLBCL patients in the bridging cohort(s) and the expansion phase, the dose and schedule of rituximab in the induction regimen will be 375 mg/m^2 on Day 1 of each 28-day cycle (Cycles 1•6). The dose and schedule in the consolidation phase will be 375 mg/m^2 every 2 months in combination with idasanutlin to explore potential benefit with consolidation treatment. For patients receiving rituximab, no alternative regimen will be explored as rituximab is only given at Day 1 in each treatment cycle and the overlapping toxicities with idasanutlin are expected to be less pronounced.*

Idasanutlin MBP-formulation PK exposure, PD effects (e.g., MIC-1, as a p53 activation marker), and target-mediated hematologic changes (platelet reduction in particular) were evaluated to support the optimal dosing schedule. Weekly, 3-day, and 5-day schedules were tested with weekly higher doses not activating PD marker MIC-1. The 3-day dosing did not achieve steady state and did not alleviate thrombocytopenia; therefore, a 5-day schedule was chosen.

The MTD for solid tumors, including patients with NHL, has been determined as 500 mg BID • 3 days or 500 mg QD • 5 days with MBP formulation. The QD • 3 days dose regimen did not achieve steady-state exposure in solid tumors, and NHL achieved a clinically relevant shorter period of SD but did not alleviate thrombocytopenia. Since a relatively low dose is to be initiated, QD of two 50-mg tablet has been chosen. As the dose escalation increases, the “pill burden” may require BID administration beyond the 400-mg QD dose SDP formulation for dose escalation.

The PK results from SDP food-effect study of 19 evaluable patients in Study NP28902 (all patients received three crossover treatments) showed that there was little evidence for a food effect. For the high-fat meal, there was equivalence demonstrated in all PK exposure parameters analyzed with 90% CI values, while the low-fat meal demonstrated <20% increase in all PK exposure parameters analyzed and were just outside the upper limit of 90% CI for bioequivalence. However, this increase is unlikely to be clinically

significant as the interpatient PK variability regardless of food is approximately 50%. As such, patients will take idasanutlin with their own choice of fed or fast.

